Interventions	Continue Group Patients in the continue group will continue with their ACE-I and/or ARB 72 hours prior to the day of surgery and continue for at least 48 hours after surgery. Stop Group Patients in the stop group will stop their ACE-I and/or ARB [according to half-life of each individual drug] prior to the day of surgery through to at least 48 hours after surgery.

Primary outcome measure	The primary outcome is myocardial injury, a binary variable based on plasma high sensitivity Troponin-T measured in blood samples collected immediately before the induction of anaesthesia, and then postoperative day 1± 6 hours and day 2±6 hours. The primary outcome is met under the following conditions: • Troponin-T ≥15 ng/L within 48 hours after surgery with a pre-operative value <15 ng/L OR • Troponin-T increase ≥5 ng/L within 48 hours after surgery with a pre-operative value ≥15ng/L

3. Outcome measures

Primary outcome measure

The primary outcome is myocardial injury, a binary variable based on plasma high sensitivity Troponin-T) measured in blood samples collected immediately before the induction of anaesthesia, and then postoperative day 1 ± 6 hours and day 2 ± 6 hours after surgery. The primary outcome is met under the following conditions:

- Troponin-T ≥15 ng/L within 48 hours after surgery with a pre-operative value <15 ng/L OR
- Troponin-T increase ≥5 ng/L within 48 hours after surgery with a pre-operative value ≥15ng/L

Secondary outcome measures

- Peak level of Troponin-T measured within 48 hours of surgery. Peak Troponin-T level (ng/L) will be calculated as the highest Troponin-T from the blood samples collected at 24 hours and 48 hours after surgery.
- Infection within 30 days of surgery
- Myocardial infarction within 30 days of surgery
- Acute heart failure within 30 days of surgery
- Stroke within 30 days of surgery
- Death within 30 days of surgery

Full definitions of secondary outcome measures can be found in the SPACE protocol.

4. Sample size and randomisation

Sample size calculation

Assuming incidence of postoperative myocardial injury of 50% in patients undergoing major surgery in the cessation group, a sample size of 248 patients will provide 90% power to detect as statistically significant (p<0.05) an 20% absolute risk reduction to 30% [1, 2]. Allowing for 5% withdrawal/loss to follow up, we will aim to recruit a total of 260 patients.

Randomisation procedure

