Randomisation will occur after the participant has provided informed consent 72 hours before the surgical procedure is due to start. Participants are randomised to a treatment group in a 1:1 ratio using a computer-generated dynamic procedure (minimisation) with a random component. Minimisation variables are trial centre, surgical procedure category (surgery involving the gut and all other surgery) and ACE-I and/or ARB category. Each participant will be allocated with 80% probability to the treatment group that minimises between group differences in these factors among all participants recruited to the trial to date, and to the alternative group with 20% probability. To enter a patient into the SPACE trial, research staff at the site will log on to a secure web-based randomisation and data entry platform hosted by Queen Mary University of London and complete the patient's details to obtain a unique patient identification number and allocation to a treatment group. A patient's treatment group allocation will only be revealed to the person performing randomisation.

5. Analysis methods

General analysis principles

Analyses will follow the intention-to-treat principle: all randomised patients with a recorded outcome will be included in the analysis and analysed according to the treatment to which they were randomised [3, 4]. Patients will be included in the analysis, regardless of whether the treatment they received was compliant with the protocol. Definitions of what constitutes a recorded outcome for each outcome can be found in Appendix 1. Patients with missing outcome data will be excluded from the analysis. Missing data for baseline covariates to be included in the analysis model will be accounted for using mean imputation for continuous variables and the missing indicator approach will be used for missing data for categorical variables [5, 6].

For the analysis of the primary outcome, each secondary outcome, and all process measures, we will present the following information:

- The number of patients included in each analysis, by treatment group
- A summary statistic of the outcome (e.g. mean (SD), number (%)), by treatment group
- The estimated treatment effect
- A 95% confidence interval for the estimated treatment effect
- A two-sided p-value

For all analyses, a significance level of 5% will be used.

Representativeness of patients

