Myocardial infarction within 30 days of surgery

Equal to 1 if:

Myocardial infarction is marked under Clavien-Dindo grade I-V

Equal to 0 if:

• Myocardial infarction is marked as "None"

Missing if:

Myocardial infarction is missing

Acute heart failure within 30 days of surgery

Note in the CRF acute heart failure is known as Cardiogenic pulmonary oedema Equal to 1 if:

• Cardiogenic pulmonary oedema is marked under Clavien-Dindo grade I-V

Equal to 0 if:

• Cardiogenic pulmonary oedema is marked as "None"

Missing if:

• Cardiogenic pulmonary oedema is missing

Stroke within 30 days of surgery

Equal to 1 if:

• Stroke is marked under Clavien-Dindo grade I-V

Equal to 0 if:

• Stroke is marked as "None"

Missing if:

Stroke is missing

Death within 30 days of surgery

Equal to 1 if:

- Patient status at 30-day follow-up is dead
- AND date of death is within 30 days of surgery

Equal to 0 if:

[figure not shown]
- Patient status at 30-day follow-up is alive
- OR patient status at 30-day follow-up is marked as 'dead' and date of death is not within 30 days of surgery

Missing if:

- Patient status at 30-day follow-up is missing
- Patient status at 30-day follow-up is marked as 'dead' and missing date of death

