Anastomotic leak					
Perforation of viscus					
Gastro-intestinal bleed					
Other postoperative haemorrhage					
Any other complication					
Acute kidney Injury - no. (%)					

Table 6: Process measures

Process measures		Number of patients with available data - no. (%)		Summary measure	
	Stop (n=XXX)	Continue (n=XXX)	Stop	Continue	
Re-admission to hospital within 30 days of surgery – no. (%)					
Duration of hospital stay after surgery (days)					
Mean (SD)					
Median (IQR)					
Number of patients admitted to a critical care unit - no. (%)					
Total duration of critical care stay within 30 days of surgery (days)					
Mean (SD)					
Median (IQR)					

Table 7:Adverse events

Adverse Events - no. (%)	Stop (n=XXX)	Continue (n=XXX)
Patients with ≥ 1 adverse event		
Total number of adverse events		
Number of adverse events per patient		
0		
1		
2		
3		
Type of adverse event		
Hypertension ^a		
Hypotension ^b		
Acute kidney injury ^c		
Other		

^a Defined as Systolic BP>180mmHg from randomisation until 48 hours after surgery, Diastolic BP> 100mmHg from randomisation until 48 hours after surgery

Table 8: Serious Adverse Events

Serious Adverse Events	Stop (n=XXX)	Continue (n=XXX)
Patients with ≥1 SAE		
Total number of SAEs		
Type of SAE		
Death		
Life-threatening complication		
Prolonged existing hospital stay or required re-		
admission		
Significant disability or incapacity		
Other important medical event		

^b Defined as requiring pressor via central venous access from randomisation until 48 hours after surgery

^c Defined as in the absence of haemorrhage/sepsis (KIDIGO grades 1-4) within 30 days after surgery

Table 9: Revised Cardiac Risk Index for Pre-Operative Risk

Revised Cardiac Risk Index for Pre-Operative	Number of patients with available data - no. (%)		Summary measure	
Risk	Stop (n=XXX)	Continue (n=XXX)	Stop	Continue
Score - no. (%)				
0 - 2				
3 - 6				
Components - no. (%)				
Elevated-risk surgery				
History of ischemic heart disease				
History of congestive heart failure				
History cerebrovascular disease				
Pre-operative treatment with insulin				
Pre-operative creatinine > 2 mg/dL / 176.8 mcmol/L

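### The rule for 30-day death, read literally, codes a randomised patient who dies before surgery as a non-event

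*SAP*

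**What the plan says.** **Timing of randomisation and treatment.** SAP section 4 (Randomisation procedure) states: "Randomisation will occur after the participant has provided informed consent 72 hours before the surgical procedure is due to start". Under Interventions in section 2, stop-group patients are off their drug from a point set by its half-life, "prior to the day of surgery through to at least 48 hours after surgery". Continue-group patients "will continue with their ACE-I and/or ARB 72 hours prior to the day of surgery". The regimens therefore differ before the operation.

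**Outcome.** Section 3 lists "Death within 30 days of surgery" as a secondary outcome. Infection, myocardial infarction, acute heart failure and stroke have the same surgery-based window.

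**Coding of death (Appendix 1).**
- 1 if follow-up status is dead "AND date of death is within 30 days of surgery".
- 0 if status is alive, "OR patient status at 30-day follow-up is marked as 'dead' and date of death is not within 30 days of surgery".
- Missing if the 30-day status is missing, or if the patient is dead without a recorded date.

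No rule names a patient who dies before surgery or who never has surgery.

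**Analysis population.** Section 5 commits to intention to treat: "all randomised patients with a recorded outcome will be included in the analysis and analysed according to the treatment to which they were randomised".

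**Adverse events.** In Appendix 3, Table 7 counts hypertension and hypotension from randomisation. The footnote for hypotension reads: "Defined as requiring pressor via central venous access from randomisation until 48 hours after surgery". The same table times acute kidney injury from surgery.

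**The concern.** A rule meant to separate deaths inside the window from later ones has been written without a direction. It asks only whether the date falls inside a period counted from surgery, and sends every other dated death to 0. A death between randomisation and surgery is also outside that period, yet it happens after allocation and possibly after the regimens have diverged. Coding it 0 would place a patient known to have died among the survivors of the arm to which he or she was randomised.

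The mortality row of Table 4 is at stake, together with its agreement with the death row of the serious adverse event table (Table 8). Section 5 also makes a formal analysis of death conditional on at least 10 events, so with counts near that threshold a single code can decide whether a test is run.

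**Working it through.** **Step 1: the plan's own figures.** The SAP gives no expected rate for any 30-day outcome. Its only figure to reproduce is the primary-outcome sample size, with inputs from section 4 (50% against 30%, 90% power) and section 5 (two-sided 5%). With pooled variance and no continuity correction:

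n per arm = [1.960 × √(2 × 0.4 × 0.6) + 1.282 × √(0.5 × 0.5 + 0.3 × 0.7)]² / 0.20² = 124, so 248 in total, as stated.

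The present point does not depend on it. It supplies only the recruitment target of 260, which is 130 per arm at 1:1 allocation.

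**Step 2: apply the Appendix 1 death rule to a patient who dies between randomisation and surgery.**
- Status dead, date recorded, no operation took place: the death is not inside 30 days of any surgery, so the code is 0. This is the most literal result.
- Same patient, but the planned surgery date is substituted and the 30 days are read in both directions: the code is 1.
- No 30-day status entered because there was no operation: the code is missing, and the patient leaves the analysis.

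One patient can thus receive any of three codes, and the SAP does not choose between them. For a death after day 30 the rule gives 0, as it should.

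**Step 3: the other clinical outcomes.** Myocardial infarction, acute heart failure and stroke are 1 if the case report form item carries a Clavien-Dindo grade and 0 if it is marked as none. No date enters the rule. A preoperative event would be 1 if someone marked it. The outcome name suggests that it should not be marked, and the rule itself is silent on when the window opens.

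**Step 4: size.** One death in an arm of 130 is 1/130 = 0.77 percentage points. Counting from randomisation lengthens the window from 30 to about 33 days, of which 3/33 = 9.1% lies before surgery. As an assumption, let the preoperative hazard equal the 30-day postoperative average. With 30-day mortality r, the expected number of deaths before surgery among 260 patients is 260 × [1 − (1 − r)^(3/30)]:
- r = 1%: 0.26 before surgery, 2.6 after.
- r = 2%: 0.52 before surgery, 5.2 after.
- r = 4%: 1.06 before surgery, 10.4 after.

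A lower preoperative hazard gives fewer, and a higher one more.

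**The case against.** The strongest reply is that the line was evidently written for deaths after day 30, and that timing outcomes from surgery suits a secondary objective framed as postoperative morbidity. Both parts stand. A surgery-based window is a legitimate design choice, and three of the six infection components are surgical site infections, which cannot precede an operation. Neither part settles how a preoperative death is coded.

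Several stronger readings are tempting, and the SAP does not support them:
- *That every preoperative event is excluded.* A reader might infer this from the outcome names. For myocardial infarction, heart failure and stroke, no coding rule excludes an event by date. The SAP refers to the protocol for full definitions, and the protocol was not available for this check.
- *That patients whose surgery is cancelled have no defined outcome.* Status alive gives 0 for death, and items marked as none give 0. Neither rule needs a surgery date.
- *That Table 7 shows an inconsistency.* It shows that the SAP treats the preoperative interval as on-study time for some events. Acute kidney injury in the same table runs from surgery, so mixed windows are part of the plan.
- *That intention to treat is broken.* Both arms share the same window, and patients are analysed as allocated. Coding a known death as survival fits poorly with the principle, but it is not a formal breach of it.
- *That the comparison is biased towards stopping.* This presupposes preoperative harm from stopping. An uncounted death could fall in either arm.
- *That such deaths go unreported.* Table 8 has a row for death. Its start of counting is not stated, but nothing excludes preoperative deaths.

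**Conclusion.** The point holds for death. As written, the rule most literally turns a randomised patient who dies before surgery into a non-event, and it can also yield 1 or missing. For myocardial infarction, acute heart failure and stroke the defect is narrower: the start of the window is not stated.

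The likely size is small, about 0 to 1 deaths in the whole trial. That rests on assumed mortality of 1% to 4%, a constant hazard and a 72-hour interval, none of which the SAP supports with data. The consequence per patient is 0.77 points in one arm, in a direction that cannot be predicted. With fewer than 10 deaths, only counts will be shown and no test is affected. The correction is worth making because it is cheap and a known death should not be tabulated as survival.

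**What to change.** 1. In section 3 and Appendix 1, define death as occurring from randomisation to 30 days after surgery, or to 30 days after the planned surgery date if no operation takes place.
2. Code a dead patient 0 only when the date of death is later than the end of that window.
3. Report by arm, beside the 30-day outcomes in Table 4, any myocardial infarction, acute heart failure or stroke between randomisation and surgery.
4. Leave infection and the troponin outcomes timed from surgery.

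The cost is a few lines of text. The label of the mortality outcome changes and must be kept consistent with the protocol. Preoperative events would come from adverse event and serious adverse event records, not from the outcome form, so the two sources should be distinguished in a table footnote. That is a reason to list preoperative non-fatal events separately instead of merging them into the graded outcomes. The SAP states that version 2.0 was written after its statistician had access to allocation data, so the change and its reason should be entered in the revision history.

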Appendix 2: Information for CONSORT flow diagram

The following information will be provided in the CONSORT flow diagram:

Appendix 3: Dummy tables

Table 1: Baseline Characteristics

		f patients with data - no. (%)	Summary measure		
Baseline Characteristics	Stop (n=XXX)	Continue (n=XXX)	Stop	Continue	
Gender - no. (%)					
Male					
Female					
Age (years)					
Mean (SD)					
Median (IQR)					
Current Smoker - no. (%)					
American Society of Anaesthesiology grade - no. (%)					
III					
IV					
Chronic comorbid disease - no. (%)					
COPD					
Asthma					
Interstitial lung disease or pulmonary disease					
Ischaemic heart disease					
Diabetes mellitus					
Heart failure					
Liver cirrhosis					
Active cancer					
Stroke or transient ischaemic attack (TIA)					
Peripheral vascular disease					
Hypertension					
Any treated infections within the previous month					
Planned surgical procedure - no. (%)					
Surgery involving the gut					
All other surgery					
Class of drug routinely taken - no. (%)					
ACE-I					
ARB					
Trial Centre - no. (%)					
County Durham and Darlington NHS Foundation					
Trust					
Plymouth Hospitals NHS Trust					
Barts Health NHS Trust					
University College London Hospitals					
University Hospitals Bristol NHS Foundation Trust					
Surgical procedure performed - no. (%)					
Surgery involving the gut					
All other surgery					
Pre-operative blood tests results					
Haemoglobin (d/DL)					
Mean (SD)					
Median (IQR)					
Creatinine (µmol/L)					
Mean (SD)		'			

Median (IQR)		
Cardiovascular medication - no. (%)		
Beta-blocker		
Calcium channel antagonist		
Doxazosin		
Diuretic		
Statin		
Nitrate		
Anti-platelet agents		
ACE-I/ARB drugs		

Abbreviations: SD, standard deviation; IQR, Interquartile range; COPD, chronic obstructive pulmonary disease.

Table 2: Clinical management

	-	patients with ata - no. (%)	Summary measure	
Clinical management characteristics	Stop (n=XXX)	Continue (n=XXX)	Stop	Continue
Surgical technique - no. (%)				
Open surgical technique used during surgery				
Laparoscopic or laparoscopic assisted technique				
Laparoscopic converted to open				
Anaesthetic technique - no. (%)				
General anaesthesia alone				
General anaesthesia + epidural				
General anaesthesia + spinal				
General anaesthesia + other regional				
Regional anaesthesia + sedation				
Endotracheal tube inserted				
Planned level of care on the first night after surgery - no. (%)				
Critical care unit level 3				
Critical care unit level 2				
Post-anaesthesia care unit				
Surgical ward				
Actual level of care on the first night after surgery - no. (%)				
Critical care unit level 3				
Critical care unit level 2				
Post-anaesthesia care unit				
Surgical ward				
Blood pressure during surgery				
Systolic blood pressure <90 mmHg - no. (%)				
Phenylephrine, total dose during surgery (mcg)				
Median (IQR)				
Ephedrine, total dose during surgery (mg)				
Median (IQR)				
Metaraminol, total dose during surgery (mg)				

Median (IQR)		
Other pressor support - no. (%)		
Arrhythmias - no. (%)		
Intravenous fluids during surgery		
Total volume of intravenous fluid administered excl. blood products (MI/kg/h)		
Median (IQR)		
Total volume of blood products administered (mL)		
Median (IQR)		
Lactate end of surgery mmol/L		
Median (IQR)		

Abbreviations: SD, standard deviation; IQR, Interquartile range

Table 3: Adherence and contamination

Adherence and contamination - no. (%)	Stop (n=XXX)	Continue (n=XXX)
Patients with ≥1 treatment deviation		
Total number of deviations		
Number of treatment deviations per patient		
0		
1		
2		
Patient in the stop group did receive ACE-I and/or ARB		N/A
Patient in the continue group did not receive ACE-I and/or ARB	N/A	
Other deviation		

Table 4: Primary and secondary outcomes.

Outcomes	available included in	Number of patients with available data and included in analysis - no. (%)		Summary measure		P- value
	Stop (n=XXX)	Continue (n=XXX)	Stop	Continue	(95% CI)	
Primary outcome						
Myocardial injury ^a						
Secondary outcomes						
Peak hsTnT ^a						
Infection ^b						
Myocardial infarction ^b						_
Acute heart failure ^b						
Stroke ^b						
Death ^b						

^a Within 48 hours of surgery

b Within 30 days of surgery

Table 5: Complications within 30 days of surgery

		patients with ata - no. (%)	Summary measure		
Complication	Stop (n=XXX)	Continue (n=XXX)	Stop	Continue	
Cardiac - no. (%)					
Arrhythmia					
Cardiac arrest with resuscitation					
Respiratory - no. (%)					
Pneumonia					
Pleural effusion					
Pneumothorax					
Bronchospasm					
Aspiration pneumonitis					
Acute lung injury					
Acute respiratory distress syndrome					
Infection - no. (%)					
Surgical site infection (superficial)					
Surgical site infection (deep)					
Surgical site infection (organ space)					
Urinary tract infection					
Infection, source uncertain					
Laboratory confirmed blood stream infection					
Other - no. (%)					
Pulmonary embolism					
Acute psychosis or delirium					
Bowel infarction					
Anastomotic leak					
Perforation of viscus					
Gastro-intestinal bleed					
Other postoperative haemorrhage					
Any other complication					
Acute kidney Injury - no. (%)					

Table 6: Process measures

Process measures		Number of patients with available data - no. (%)		Summary measure	
	Stop (n=XXX)	Continue (n=XXX)	Stop	Continue	
Re-admission to hospital within 30 days of surgery – no. (%)					
Duration of hospital stay after surgery (days)					
Mean (SD)					
Median (IQR)					
Number of patients admitted to a critical care unit - no. (%)					
Total duration of critical care stay within 30 days of surgery (days)					
Mean (SD)					
Median (IQR)					

Table 7:Adverse events

Adverse Events - no. (%)	Stop (n=XXX)	Continue (n=XXX)
Patients with ≥ 1 adverse event		
Total number of adverse events		
Number of adverse events per patient		
0		
1		
2		
3		
Type of adverse event		
Hypertension ^a		
Hypotension ^b		
Acute kidney injury ^c		
Other		

^a Defined as Systolic BP>180mmHg from randomisation until 48 hours after surgery, Diastolic BP> 100mmHg from randomisation until 48 hours after surgery

Table 8: Serious Adverse Events

Serious Adverse Events	Stop (n=XXX)	Continue (n=XXX)
Patients with ≥1 SAE		
Total number of SAEs		
Type of SAE		
Death		
Life-threatening complication		
Prolonged existing hospital stay or required re-		
admission		
Significant disability or incapacity		
Other important medical event		

^b Defined as requiring pressor via central venous access from randomisation until 48 hours after surgery

^c Defined as in the absence of haemorrhage/sepsis (KIDIGO grades 1-4) within 30 days after surgery

Table 9: Revised Cardiac Risk Index for Pre-Operative Risk

Revised Cardiac Risk Index for Pre-Operative	Number of patients with available data - no. (%)		Summary measure	
Risk	Stop (n=XXX)	Continue (n=XXX)	Stop	Continue
Score - no. (%)				
0 - 2				
3 - 6				
Components - no. (%)				
Elevated-risk surgery				
History of ischemic heart disease				
History of congestive heart failure				
History cerebrovascular disease				
Pre-operative treatment with insulin				
Pre-operative creatinine > 2 mg/dL / 176.8 mcmol/L
